**3.14 Obtain copies of all study-related correspondence with the FDA, when needed.**

**3.15 Communicate deviations from the protocol, GCPs, or regulatory requirements to the investigator and taking appropriate action to prevent recurrence of the deviations.** To accomplish this, the monitor will:

- Verify subject visits have taken place as stated in protocol by checking the subject tracking log.
- Verify all tests have been completed as stated in the protocol by looking at source documentation and CRFs.
- Verify any noncompliance issues with protocol (subject) by looking at CRFs and other source documentation.
- Verify if any visit was out of allowable time deviation by looking at subject visit schedule.
- Verify any other deviations by comparing the protocol with source documentation and/or subject CRFs.

***Extent of Data Monitoring***

Monitors will review clinical data that affect study endpoints defined in the protocol. Data collected for reasons other than to support protocol-defined endpoints will not be monitored.

The extent of subject data monitoring will include verifying:

- Initial study consent : 100% of enrolled subjects;
- Study eligibility : 100% of enrolled subjects;
- Data to support protocol defined endpoints : 100% of completed subjects

In addition to monitoring subject data, the monitor will review the regulatory file for any additions to GCP-required documents since the last visit. Monitors will, at their first and last monitoring visits, review the regulatory file for the presence, completeness, and accuracy of all GCP-required documents.

***Transfer of Monitoring Obligation Agreement***

A signed Transfer of Monitoring Obligation Agreement will be obtained from all sponsors and principal investigators, if applicable.

***Site Visit Confirmation***

After scheduling a monitoring visit with the site the following will occur:

- The monitor will review previous monitoring reports to identify any unresolved issues.

***Debriefing the Investigator***

At the end of each monitoring visit, the monitor will meet with the investigator or coordinator to go over any findings of the visit.

### ***Documentation of Findings***

The monitor will send a monitoring report to the study sponsor and to the study investigator. A copy of every monitoring report will be retained by the sponsor and the monitor.

The monitoring report will describe the progress of the study, the findings of the visits, unresolved issues, and follow-up required. The monitor will keep an electronic copy of the report and a signed copy will be maintained in the Regulatory file. Follow-up items will be checked and documented at the next monitoring visit. The report will include, but will not be limited to, the following:

- A list of records reviewed, i.e. subject charts, hospital records, lab slips, etc.;
- Number of case report forms reviewed by research subject number and visit date;
- Statement that test article accountability records were or were not sufficient;
- Statement regarding whether there was any evidence of under-reporting of adverse events;
- Statement regarding protocol adherence

*(FDA Compliance Program Guidelines, Part III)*

### ***Frequency of Visits***

The monitor will provide monitoring before, during, and at the end of clinical trials.

In general, monitoring visits should be scheduled according to a “risk-based monitoring” approach as found in FDA guidance (August 2013).

The following schedule can be used as a suggestion:

- *Site Initiation Visit (SIV)*: After IRB approval but prior to enrolling the first subject;
- *First monitoring visit*: As soon as possible after the first subject is enrolled;
- *Risk-based interim monitoring visits (IMV)*: as needed based on risk, or about 3 weeks after first subject is enrolled;
- *Close-out visit (COV)*: After the last subject has completed his/her participation in the study.

This monitoring schedule may be revised based on the following considerations:

- Accrual rate
- History of protocol deviations or non-compliance with GCPs
- Number of data corrections required
- Study stage (e.g. start-up or follow-up)
- Complexity of the trial
- IRB request

### ***Interface with the Office of Regulatory Affairs***

The monitor will report the following situations, should they occur, to the Office of Research Compliance and Regulatory Affairs:

- Persistent failure by the sponsor, investigator, or other member of the study team to follow the protocol;
- Persistent failure by the sponsor, investigator, or other member of the study team to follow GCP guidelines;

BQL	Below Quantification Limit
CFP	Color Fundus Photograph
CI	Confidence Interval
CNV	Choroidal Neo Vascularization
CSR	Clinical Study Report
DBL	Database Lock
DMC	Data Monitoring Committee
ECG	Electrocardiogram
eCRF	Electronic Case Report Form
ETDRS	Early Treatment Diabetic Retinopathy Study
EVA	Electronic-ETDRS Visual Acuity
FA	Fluorescein Angiography
FAF	Fundus Autofluorescence
FAS	Full Analysis Set
FRI	Functional Reading Independence Index
GA	Geographic Atrophy
HCT	Hematocrit
HDL	High-density Lipoprotein
HGB	Hemoglobin
INN	International Nonproprietary Names
IOP	Intraocular Pressure
IReST	International Reading Speed Test
ITT	Intent to Treat
LDL	Low-density Lipoprotein
LLD	Low Luminance Deficit
LLOQ	Lower Limit of Quantification
LLVA	Low Luminance Visual Acuity
LMEM	Linear Mixed-Effects Model

LS	Least Squares
MCH	Mean Corpuscular Hemoglobin
MCMC	Markov-Chain Monte-Carlo
MCV	Mean Corpuscular Volume
MAR	Missing at Random
MM	Multi-Modal Assessment
MMRM	Mixed Model for Repeat Measures
MNAR	Missing Not at Random
MNREAD	Minnesota low vision reading chart
MOP	Manual of Performance
MRS	Maximum Reading Speed
OCT	Optical Coherence Tomography
PI	Principal Investigator
PK	Pharmacokinetics
PLT	Platelets
PP	Per Protocol
PT	Preferred Term
QTc	Corrected QT Interval
RBC	Red Blood Cell count
RPD	Reticular Pseudo Drusen
SAE	Serious Adverse Event
SAP	Statistical Analysis Plan
SD	Standard Deviation
TEAE	Treatment Emergent Adverse Event
TTO	Time Trade-Off
USAN	United States Adopted Names
VA	Visual Acuity
VFQ-25	Visual Function Questionnaire 25
WBC	White Blood Cell count
wpm	Words per Minute

1.0. INTRODUCTION

This Statistical Analysis Plan (SAP) describes the statistical methodology and data handling for the study ALK001-P3001, A Phase 2/3 Multicenter, Randomized, Double-masked, Parallel-group, Placebo-controlled Study to Investigate the Safety, Pharmacokinetics, Tolerability, and Efficacy of ALK-001 in Geographic Atrophy (GA) Secondary to Age-related Macular Degeneration (AMD). This SAP is based on protocol ALK001-P3001 version 1.1, dated 01Feb2019. This SAP was prepared prior to database lock and unmasking. Any deviations from this SAP will be documented in the Clinical Study Report (CSR).

The trial consists of a treatment period of 24 months and is designed to obtain evidence on the effects of gildeuretinol acetate, also named “ALK-001” in this plan, on the mean rate of growth (slope) estimated based on GA area and measured on fundus autofluorescence (FAF) imaging.

The following guidelines were used as a guide to write this plan:

- ICH E3 structure and content of clinical study reports
- ICH E9 statistical principles for clinical trials
- ICH E9 (R1) addendum on estimands and sensitivity analysis in clinical trials to the guideline on statistical principles for clinical trials

2.0. STUDY OBJECTIVES AND ENDPOINTS

2.1. Study Objectives

2.1.1 Primary Objective

- To assess the effects of ALK-001 on the growth rate of GA area after 24 months of treatment in subjects with GA secondary to AMD.

2.1.2 Key Secondary Objectives

To evaluate the effects of ALK-001 compared to placebo in subjects with GA secondary to AMD with respect to:

- Low luminance visual acuity (LLVA) score
- Best-corrected visual acuity (BCVA) score

2.1.3 Secondary Objectives

To evaluate the effects of ALK-001 compared to placebo in subjects with GA secondary to AMD with respect to:

- The growth rate of GA lesion(s) between baseline and Month 12
- The growth rate of GA lesion(s) between Month 12 and Month 24
- The growth rate of GA lesion(s) between Month 6 and Month 24
- Low luminance deficit (LLD) score

- Maximum reading speed, as measured by Minnesota Reading (MNRead)
- Binocular reading speed, as measured by International Reading Speed Test (IReST)
- Functional Reading Independence (FRI) Index score
- Visual Functioning Questionnaire 25 Item Version (VFQ-25)
- Incidence of CNV in eyes with GA, when the fellow eye has CNV at baseline

2.1.4 Safety and Pharmacokinetics Objectives

- To assess the safety and tolerability of ALK-001
- To assess the pharmacokinetics of ALK-001

2.1.5 Exploratory Objectives

To evaluate the effects of ALK-001 compared to placebo in subjects with GA secondary to AMD with respect to:

- Retinal function
- Incidence of CNV in eyes with GA, when the fellow eye has intermediate AMD at baseline
- Incidence of advanced AMD (CNV or GA) in the fellow eye, when the fellow eye has intermediate AMD at baseline

2.2. Endpoints

2.2.1 Primary Efficacy Endpoint

- Growth rate of the total area of GA lesion(s) between baseline and Month 24, as measured on fundus autofluorescence (FAF)

2.2.2 Key Secondary Efficacy Endpoints

The key secondary endpoints include:

- Change from baseline in LLVA score at Month 24 as assessed by either Early Treatment Diabetic Retinopathy Study (ETDRS) chart, or an Electronic-ETDRS Visual Acuity (EVA) system (number of letters)
- Change from baseline in BCVA score at Month 24 as assessed by either ETDRS chart or an EVA system (number of letters)

2.2.3 Secondary Efficacy Endpoints

- Growth rate of the total area of GA lesion(s) between baseline and Month 12
- Growth rate of the total area of GA lesion(s) between Month 12 and Month 24
- Growth rate of the total area of GA lesion(s) between Month 6 and Month 24

- Change from baseline in LLD score
- Change from baseline in maximum reading speed at Month 24, as measured by MNRead (wpm)
- Change from baseline in binocular reading speed, as measured by IReST
- Change from baseline in FRI Index score at Month 24
- Change from baseline in VFQ-25 total score
- Incidence of CNV in the study eye, when the fellow eye has CNV at baseline

2.2.4 Safety and Pharmacokinetics Endpoints

- Adverse events (AEs), including serious adverse events (SAEs)
- Laboratory tests (hematology, biochemistry, lipids)
- Vital signs
- 12-lead electrocardiography (ECG)
- Physical examination
- Ocular exam and intraocular pressure (IOP)
- Pharmacokinetics: absolute concentration and percentage of deuterated vitamin A in plasma

2.2.5 Exploratory Endpoints

- Changes in retinal sensitivity, as measured by fundus-tracking microperimetry (Nidek MP1)
- Incidence of CNV in the study eye, when the fellow eye has intermediate AMD at baseline
- Incidence of advanced AMD (CNV or GA) in the fellow eye, when the fellow eye has intermediate AMD at baseline

3.0. STUDY DESIGN

[figure not shown]
3.1. Overall Study Design

This is a randomized, double-masked, parallel-group, multicenter study evaluating the safety and efficacy of ALK-001 in subjects with GA secondary to AMD.

Approximately 300 subjects were planned to be randomized in a 2:1 ratio to receive either ALK-001 at 14 mg/day or placebo daily for a total treatment duration of 24 months. There was no stratification for randomization, and subjects were randomized using random permuted blocks of size 3 and 6. Due to enrollment delays caused by COVID-19, 200 subjects were randomized with the same 2:1 randomization. Subjects, investigators and study staff, and sponsor staff who may be in contact with investigators or subjects, are masked until after this SAP is submitted to FDA and database lock has occurred.

After an initial screening day (V01), subjects are given a placebo to take once a day during a run-in period. The placebo is indistinguishable from ALK-001, and subjects are unaware that they are receiving the placebo. The run-in period typically lasts between 2 and 4 weeks. At the conclusion of the screening and run-in period, subjects who meet all eligibility criteria were randomized on Day 1 (V02).

Following randomization at V02, subjects have follow-up visits scheduled at Month 6 (V04), Month 12 (V06), Month 18 (V08), and Month 24 (V10) after starting treatment on Day 1. Treatment discontinues at Month 24 (V10). A diagram of the study design and timelines is provided below.

The follow-up visits encompass various assessments. Safety and tolerability will be assessed by monitoring AEs, clinical laboratory tests (biochemistry, hematology, lipids), vital signs, ECG, physical examinations, and pharmacokinetics. Efficacy assessments include GA area measured on FAF imaging, BCVA, LLVA, reading speed, VFQ-25, FRI, microperimetry (optionally performed at sites where available), etc. (Refer to [Appendix 1](#) for a full list of assessments and visit schedule).

Each subject's study duration is up to 2 years and 4 weeks, including screening and run-in period and the 2-year treatment. The study will end when the last subject completes Visit V10 (Month 24) or discontinues the study.

Following completion of the initial treatment period of 2 years, subjects may be given the choice to enter a two-year open-label extension study, which is not covered in this SAP.

3.2. Sample Size

The initial sample size was based on literature data on the progression of GA at the time the study was started. With 300 subjects and assuming that 80% of subjects are evaluable for the primary outcome measure, the study has an 80% power to detect, after 24 months of treatment, a 33% slowing in GA growth rate with a 2-tailed significance of 0.05, assuming a conservative standard deviation of 1.5 mm²/year and an average GA growth rate of 1.8 mm²/year in the control group.

Based upon natural history literature data updated as of the date of this SAP, and the area of GA, indicating an average GA growth rate of 1.8 mm²/year with a standard deviation of 1.2 mm²/year, with 200 subjects and considering that 80% of subjects completed the study and are expected to

have evaluable data for the primary outcome measure, the study has an 80% power to detect, after 24 months of treatment, a 33% slowing in GA growth rate with a 2-tailed significance of 0.05.

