*Patients should be deemed sufficiently healthy to complete the 24-month duration of the study. Comprehensive visits will be every 6 months with short optional safety visits every 3 months.*

2. Can patients who previously entered clinical trials participate?

*Yes.*

3. What other non-AMD conditions or drugs can cause atrophic patches?

*Several retinal diseases and dystrophies, systemic conditions, and drug-induced toxicity can cause atrophic patches that can be confused with AMD. Examples include Stargardt disease, pattern dystrophy, RPE tears, trauma, hemorrhage, drug-induced toxicity (hydroxychloroquine, didanosine, thioridazine, etc.), choroidal sclerosis, Bietti's crystalline dystrophy, etc.*

*Subjects thought to have GA secondary to any other condition than AMD will not be enrolled.*

4. Can subjects take AREDS2 supplements during the study?

*Yes, AREDS2 will be allowed and recommended for all patients, especially those with intermediate AMD in the fellow eye.*

5. Can subjects take vitamin A-containing supplements or foods containing vitamin A or beta-carotene?

*Subjects should avoid vitamin A or beta-carotene containing supplements, as well as food products containing overly high amounts of vitamin A such as liver or liver-based products/oils, giblets or other animal's internal organs, highly concentrated/processed fruit juices. All fruits and vegetables in their "natural," unprocessed form/concentration, are acceptable without restriction.*

6. What happens to patients who develop CNV in the study eye? In the fellow eye?

*Patients who develop CNV in the study eye continue the study and receive standard of care treatment as determined by each PI.*

7. Can patients with history of or active CNV enroll?

*Yes, as long as at least one eye has "pure GA" with no history of or active CNV.*

8. Are subjects stratified?

*No.*

9. What are the expected outcomes for each eye based on their respective baseline?

Study Eye	Fellow Eye	Primary outcome	Secondary outcome
Pure GA	CNV	GA growth rate in study eye	Incidence of CNV in study eye (natural hx reports approx. 20% incidence at 24 months)
Pure GA	GA with or without CNV	GA growth rate in study eye	GA growth rate in fellow eye; Incidence of CNV in study eye (natural hx reports approx. 3-6% at 24 months)
Pure GA	Intermediate AMD with RPD or large macular drusen	GA growth rate in study eye	Incidence of advanced AMD (CNV or GA) in fellow eye (natural hx reports approx. ~20% incidence at 24 months)

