#### **Primary outcome measure (endpoint):**

- Growth rate of the area of atrophic lesions between baseline and 24 months, as measured on fundus autofluorescence (FAF) imaging and verified by optical coherence tomography (OCT).

Methods of data analysis will be detailed in a Statistical Analysis Plan (SAP) prior to the performance of unmasked analyses. The SAP shall supersede this protocol in case of discrepancies with the SAP related to the choice of endpoints, power calculations, and statistical analyses. The SAP shall also be submitted to the regulatory agencies before any unmasked analyses are performed.

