#### **1.15.1 Sample Size Determination and Power Calculation**

Sample size calculation was based on review of all available literature data on the progression of GA. With 300 subjects enrolled in the study and assuming that 80% of subjects are evaluable for the primary outcome measure, the study has an 80% power to detect, after 24 months of treatment, a 33% slowing in

GA growth rate with a 2-tailed significance of 0.05, assuming a conservative standard deviation of 1.5 sqmm/year and an average GA growth rate of 1.8 sqmm/year in the control group.

As part of the exploratory measure, and assuming that 35% of enrolled subjects have a fellow eye with active or history of CNV, the study has an 80% power to detect, after 24 months, a 75% reduction in incidental progression to CNV in the study eye with a 1-tailed significance of 0.2 (Fisher's exact test).

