4.0. STATISTICAL ANALYSIS CONVENTIONS AND DEFINITIONS

4.1. Reporting Conventions

Individual subject data obtained from electronic case report forms (eCRFs), external sources, and any derived data will be presented in data listings by subject.

Continuous measures will be summarized by number of observations, minimum, first quartile (Q1), median, mean, third quartile (Q3), maximum, and standard deviation (SD). The minimum and maximum will be presented at the same level of precision (decimal point) of the measurements. Median, Q1 and Q3, and mean will be presented at one greater level of precision (decimal point) as the measurements. SD will be presented at two greater levels of precision. In general, the number of decimal places should not exceed 3 decimal places unless appropriate. Confidence intervals (CIs) will be provided with the same decimal places as the point estimate, unless otherwise specified, in the tables and listings.

Categorical (including binary) measures will be summarized by count and percent. Categories for which counts are 0 will be displayed for the sake of completeness. For example, if none of the subjects discontinue due to “lost to follow-up”, this reason will be included in the table with a count of 0. A row denoted as “Missing” will be included in the count tabulations where necessary to account for dropouts or missing values. Percentages will be rounded to one decimal place, unless otherwise specified.

In general, all eyes of all subjects will be included in analyses, unless otherwise noted. The primary efficacy analysis will be conducted at a significance level of 0.05. Hypothesis testing for the key secondary objectives will be conducted with significance determined at the 0.05 level with multiple testing adjustments (Refer to [Section 6.2.1](#)). For most analyses, when a hypothesis test is performed, it will be comparing the ALK-001 and Placebo treatment arms. Confidence intervals will generally be given at a level to mimic the significance level (95% CIs for 0.05 significance level) unless otherwise noted.

Unless otherwise specified, the following treatment arms will generally be included in tables, listings, and figures:

- ALK-001: Subjects randomized to 24 months of ALK-001 at 14 mg per day
- Placebo: Subjects randomized to 24 months of placebo

All analyses will be conducted in SAS®, Version 9.4 or higher (SAS Institute Inc., Cary, NC) or in R, Version 3.6.0 or higher (R Core Team 2019).

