6.0. EFFICACY ANALYSIS

Efficacy analysis including primary, key secondary, secondary, and exploratory analysis will be performed primarily using the Full Analysis Set (FAS), with subjects grouped according to the treatment assigned at randomization. Available data from all randomized subjects regardless of adherence to the protocol will be included in the efficacy analyses; this includes data from subjects who discontinued study drug early but continued with study assessments.

Unless otherwise noted, hypothesis testing and estimation of treatment effects will be performed with a mixed effect model that includes data from two treatment arms: ALK-001 and Placebo. All hypothesis tests for efficacy endpoints will be two-sided.

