6.3.5 Incidence of CNV in the Study Eye

The number and percentage of subjects with incidence of CNV in the study eye, when the fellow eye has CNV at baseline, and 95% exact CI will be generated for each treatment arm. The proportion difference among the treatment groups, and the associated 95% Wald CI and Fisher's exact test p-value will also be provided.

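### The protocol's 80% power for CNV incidence was calculated for 300 subjects and is neither restated nor withdrawn for the 200 randomised; the Wald interval planned for the same endpoint is also a poor choice

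*SAP*

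**What the plan says.** Protocol 1.15.1 gives two power statements for 300 enrolled subjects. The second reads: "the study has an 80% power to detect, after 24 months, a 75% reduction in incidental progression to CNV in the study eye". It uses a one-sided Fisher test at 0.2 and takes 35% of subjects to have CNV in the fellow eye. The control rate is in Protocol 1.5.8.2 and in the synopsis FAQ: "natural hx reports approx. 20% incidence at 24 months". Protocol 1.5.4.4 and 1.5.8.2 repeat the CNV power claim without tying it to 300 subjects.

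SAP 3.1 reports that "200 subjects were randomized with the same 2:1 randomization". SAP 3.2 then gives a new power for the primary endpoint, "with 200 subjects and considering that 80% of subjects completed the study", and says nothing about CNV. Incidence of CNV in the study eye when the fellow eye has CNV stays on the list of secondary efficacy endpoints (SAP 2.2.3). SAP 6.3.5 analyses it with exact intervals within each arm, a Fisher p-value, and the difference in proportions "and the associated 95% Wald CI".

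Two rules bear on how these fit together. Under Protocol 1.6.1 the SAP prevails over the protocol on discrepancies "related to the choice of endpoints, power calculations, and statistical analyses". SAP 6.0 states: "All hypothesis tests for efficacy endpoints will be two-sided". On the level, SAP 4.1 says: "The primary efficacy analysis will be conducted at a significance level of 0.05". It sets the same level for the key secondary tests. SAP 6.3.5 names no level for CNV.

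**The concern.** The cut from 300 to 200 subjects affects both powered comparisons, but the SAP updates only one. The precedence rule works where the two documents differ. A SAP that is silent on CNV power puts nothing in place of the 80%. A null CNV result would then be read against a power that the trial does not have.

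The interval is a separate matter. Only about 2 events on ALK-001 and 4 to 5 on placebo are expected. The Wald interval is known to behave badly with counts of that size, and it would be printed beside a Fisher p-value that it can contradict.

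**Working it through.** **Inputs.** Control incidence 20% and ALK-001 incidence 5% (75% reduction), from Protocol 1.15.1 and 1.5.8.2. Share with fellow-eye CNV 35%, from 1.15.1. Evaluable fraction 80%, which 1.15.1 and SAP 3.2 state for the primary outcome; applying it to CNV is an assumption. Allocation 2:1.

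**Numbers per arm (ALK-001:placebo).**
- 300 × 0.80 × 0.35 = 84, so 56:28
- 300 × 0.35 = 105, so 70:35
- 200 × 0.35 = 70, so 47:23
- 200 × 0.80 × 0.35 = 56, so 37:19

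**Power.** Sum over all tables of Bin(y; n_ALK, 0.05) × Bin(x; n_PBO, 0.20), counting the tables whose Fisher p-value is at or below the level.

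| Subjects | Split | One-sided 0.2 | Two-sided 0.2 | Two-sided 0.05 |
|---|---|---|---|---|
| 300, 80% evaluable | 56:28 | 80.2% | 74.1% | 50.4% |
| 300, all evaluable | 70:35 | 86.0% | 82.0% | 60.0% |
| 200, all evaluable | 47:23 | 75.7% | 65.9% | 43.1% |
| 200, 80% evaluable | 37:19 | 63.4% | 58.4% | 39.7% |

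The first row reproduces the protocol's 80%. Like for like, the cut to 200 costs 80.2 − 63.4 = 16.8 points with attrition, or 86.0 − 75.7 = 10.3 points without. Neighbouring integer splits at 200 subjects move these figures by at most 4.4 points, and none reaches 80%.

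**Effect needed at 200.** For about 80% power at one-sided 0.2, the reduction must be about 80% (47:23) or 90% (37:19). At two-sided 0.05 with 37:19 and no ALK-001 events, at least 3 placebo events are needed. P(X ≥ 3) for Bin(19, 0.20) = 1 − (0.0144 + 0.0685 + 0.1540) = 76.3%, so complete prevention would still fall short of 80%.

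**Sensitivity to the 35% share (200 subjects, one-sided 0.2).** Power runs from 52.2% (25% share, 80% evaluable) to 77.7% (40% share, all evaluable). Of the shares tried from 25% to 45%, only 45% with everyone evaluable passes 80% (81.0%).

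**Wald interval.** Difference ± 1.96 × √[p₁(1−p₁)/n₁ + p₂(1−p₂)/n₂]. Expected events are 47 × 0.05 = 2.4 and 23 × 0.20 = 4.6, or 37 × 0.05 = 1.9 and 19 × 0.20 = 3.8. By exact enumeration at 5% versus 20%, for 47:23 / 37:19:

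| | Wald | Newcombe | Miettinen-Nurminen |
|---|---|---|---|
| Coverage of nominal 95% | 92.3% / 90.2% | 96.4% / 96.0% | 94.6% / 95.1% |
| Fisher p ≤ 0.05, interval includes zero | 11.7% / 14.2% | 0% / 0% | 0% / 0% |
| Fisher p > 0.05, interval excludes zero | 3.3% / 0.2% | 3.2% / 0.1% | 4.0% / 2.4% |

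With 20% in both arms, Wald coverage is 93.7% / 93.6%, close to nominal.

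**Example.** 0/37 versus 3/19: the Fisher p-value is C(19,3)/C(56,3) = 969/27,720 = 0.035. The difference is −0.158 and the standard error √(0.1579 × 0.8421/19) = 0.0837, so the Wald interval is −0.322 to 0.006. It includes zero. Newcombe gives −0.376 to −0.019.

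**The case against.** The protocol's sample-size sections open from 300 subjects, and for 300 the 80% is still true. The SAP states openly that 200 were randomised and never repeats the CNV claim. The SAP also drops the one-sided 0.2 test that the 80% describes, so one can argue that the precedence rule already retires the figure. The protocol calls this power exploratory. The endpoint is outside the gated sequence, and the gated visual acuity endpoints carry no stated power at all. With enrolment finished, restating power changes no design decision. The 200-subject figures rest on an assumed share and an evaluable fraction borrowed from the primary outcome.

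Much of that is fair on weight. The fault is an omission and not a false sentence in the SAP. But two protocol sections state the CNV power without the 300 condition. Changing the sidedness lowers the power without supplying a new figure. The SAP's authors evidently thought power at 200 worth restating for the primary endpoint.

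On the interval, the weakness does not come from the smaller trial: at the planned 56:28, Wald coverage is already 92.8%. The commoner conflict errs against claiming benefit. Score intervals do not remove every conflict either. At 46:24 or 47:24 the reverse conflict (interval excludes zero, Fisher p above 0.05) is 3.4% with Newcombe against 0.1% with Wald. Total disagreement is still lower with the score intervals.

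**Conclusion.** Both parts hold. On the protocol's own one-sided 0.2 basis, CNV power at 200 subjects is about 63% to 76%, not 80%. On a two-sided 0.05 reading it is about 40% to 43%. These figures assume 20% versus 5% incidence and a 35% share, and the lower end of each range also assumes 80% evaluable for CNV. The 0.05 level is the SAP's default, not a level it states for CNV.

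The Wald interval falls about 3 to 5 points short of nominal coverage at the design rates and disagrees with a significant Fisher test in roughly one trial in eight. The exact within-arm intervals and the Fisher test are sound. The point is worth correcting but does not touch the primary analysis or the controlled testing sequence.

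**What to change.** In SAP 3.2, add one sentence. The simpler form says that the protocol's CNV power was for 300 subjects, no longer applies, and that none is claimed. The alternative restates it for 200 subjects and the two-sided test, naming the level and the evaluable fraction. It should use the masked pooled count of subjects with fellow-eye CNV at baseline (already collected, SAP 5.3) in place of the assumed 35%.

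In SAP 6.3.5, replace the Wald interval with a Newcombe or Miettinen-Nurminen score interval, and keep the exact within-arm intervals and the Fisher p-value.

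The cost is two sentences, a less favourable or withdrawn CNV power, and an interval about 4% to 5% wider on average with Newcombe. No data collection changes, and both edits can be made while the trial is masked.
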